1. Subjects: Adult patients (≥ 18 years) with two consecutive blood glucose readings of > 150 mg/dL and ≤ 300 mg/dL will be eligible for inclusion in this study. The study population will be limited to those with acute brain injury resulting in admission to the NSICU for an anticipated length of stay >48 hours and who will not have planned steroid use post-operatively. Patients with imminent brain death or refractory intracranial hypertension will not be enrolled. Pregnant (verified by urine or serum pregnancy test within 24 hours of initiation of exenatide infusion) or lactating females, and those with a history of type 1 diabetes mellitus, pancreatitis or risk factors for acute pancreatitis (i.e. ethanol abuse, gall stones), renal insufficiency (CrCL < 45 mL/min), gastroparesis, surgery on stomach, esophageous, or duodenum or those with organ transplantation will be excluded. Additionally, those presenting with diabetic ketoacidosis or hyperosmolar hyperglycemic nonketotic syndrome will be excluded. Individuals receiving steroids or planned post-operative administration, insulin infusion within 3 hours of study drug administration, long acting insulin or sulfonylureas within 24 hours of study drug administration, another investigational drug or device, or those with known allergy to any of the study protocol drugs will be excluded. Recruitment will continue until 24 subjects receive study drug and complete the study protocol.

2. Glycemic Control Protocol: All study related protocols will be conducted in the Neuroscience Intensive Care Unit (NSICU). All patients admitted to the NSICU and that meet the eligibility criteria will be approached for consent to the study. Study drug will only be administered to those subjects providing consent via legally authorized representative and meeting glycemic thresholds. The study nurse will initiate the exenatide infusion

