10.1 The following feasibility endpoints are based upon prior literature (Nice-Sugar and Exenatide Study in the Cardiac ICU):

Proportion of patients experiencing severe hypoglycemia (<40 mg/dL), Proportion of patients achieving plasma glucose goal (110-180 mg/dL), Proportion of patients experiencing nausea requiring discontinuation of exenatide therapy

10.2 The following descriptive endpoints are included for describing experience with exenatide use in the NSICU population:

Average blood glucose value during exenatide infusion (48 hours), percent time in glucose range (48 hours), mean time to reach plasma glucose goal (110-180 mg/dL), variability outcome (SD)-MADGE, mean insulin use required (units/kg body weight), proportion of subjects requiring rescue insulin infusion protocol, number of hypoglycemic episodes (<80 mg/dL)/total number of glucose measurements (48 hours), number of subjects with >1 hypoglycemic episode (<80 mg/dL)/total number of subjects (48 hours), correlation of exenatide concentrations with creatinine clearance during infusion, elimination rate constant and area under the concentration-time curve utilizing concentrations after discontinuation of infusion, side effects and adverse events (AEs and SAEs), average daily ICP and CPP during study drug infusion, number of hypotensive episodes (SBP<100 mmHg) (48 hours), number of subjects with >1 hypotensive episode/total number of subjects (48 hours). Other adverse effects will be collected specifically assessing any alterations in gastric motility.

In patients receiving invasive intracranial multimodal monitoring as part of their standard of care, the following endpoints associated with exenatide use will be described:

Percent time outside of range for energy metabolism (glucose <0.7 mmol/L and lactate:pyruvate ratio > 40), glutamate (marker of cerebral ischemia), and glycerol (marker of cell membrane degradation) parameters (48 hours).

Based upon prior literature, the prespecified criteria for determining feasibility include the following: 1) no more than 6 patients (25%) experiencing severe hypoglycemia (<40 mg/dL); 2) at least 18 patients (75%) achieving the plasma glucose goal (110-180 mg/dL); 3) no more than 6 patients (25%) experiencing nausea leading to exenatide discontinuation. These criteria will be utilized to determine whether a future efficacy trial will be pursued.

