11. Sample size and justification: A sample size was determined using prior exenatide in critically ill patients studies and patient screening information at our site. Based upon this data, we determined to enroll 24 patients who complete 48 hours of exenatide infusion and continuous glucose monitoring. In eligible patients, cerebral microdialysis monitoring will also be performed. It is estimated based on proposed eligibility criteria that 24% (n = 200) patients admitted to the NSICU will be eligible for enrollment annually. With an approximate rate of enrollment at 15 – 20%, we are confident we could enroll 30 – 40 subjects annually.

12. Data analysis plan: Prior to analysis, data will be examined for errors, outliers, and asymmetry. When appropriate, transformations will be used to reduce asymmetry. An intent-to-treat analysis (defined as all individuals consented in the study) will be utilized. Descriptive statistics will be performed. Data will be expressed as means \pm standard error (SE) or success rates and corresponding 95%CI for continuous and

dichotomous outcomes, respectively. Analyses will be completed using the statistical software package SAS, version 9.2 (SAS institute, Cary, North Carolina).

13. Ethical consideration: The consent procedures will be reviewed and approved by the Institutional Review Board. All subjects will provide written informed consent via proxy. The informed consent process will allow the proxy to gain an in-depth knowledge of the study purposes and procedures and allow them to make informed decisions about willingness to proceed. Participation is voluntary. The proxy will be encouraged to ask questions and will be assessed for adequate understanding.

Exenatide required: yes

Placebo required: no

Clinical study duration of treatment: Subjects will be exposed to exenatide treatment for 48 hours.

Clinical study dosing schedule and frequency: exenatide 50 ng/min for 30 minutes, start exenatide infusion 25 ng/min x 48 hours

Clinical study number of sites: one

Clinical study expected number of subjects screened: It is estimated based on proposed eligibility criteria that 24% (n = 200) patients admitted to the NSICU will be eligible for enrollment annually with an approximate rate of enrollment at 15-20%.

Clinical study expected number of subjects enrolled: 24

Clinical study expected number of subjects to complete study: 24

Planned Study Start Date: January 1, 2015

Planned Study End Date: June 30, 2016

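### The go/no-go limits (6 = 25%, 18 = 75%) agree only at exactly 24 patients, but the plan recruits to 24 completers, analyses all consented, and does not say which governs

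*Combined protocol and SAP*

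**What the plan says.** Section 10.1 defines the three feasibility endpoints as proportions, for example "Proportion of patients achieving plasma glucose goal (110-180 mg/dL"), without naming a denominator. The criteria at the end of section 10 then give each limit as a count with a percentage in brackets: at most 6 patients (25%) with severe hypoglycemia, "at least 18 patients (75%) achieving the plasma glucose goal (110-180 mg/dL"), and "no more than 6 patients (25%) experiencing nausea leading to exenatide discontinuation". Their purpose is explicit: "These criteria will be utilized to determine whether a future efficacy trial will be pursued".

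Three other places bear on the denominator.

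- Recruitment: Methodology 1 (Subjects) says "Recruitment will continue until 24 subjects receive study drug and complete the study protocol", and section 11 says "we determined to enroll 24 patients who complete 48 hours of exenatide infusion and continuous glucose monitoring".
- Analysis set: section 12 says "An intent-to-treat analysis (defined as all individuals consented in the study) will be utilized". It is the only analysis set in the plan, and it is not linked to the feasibility criteria.
- Dosing: under Methodology 2 (Glycemic Control Protocol), "All patients admitted to the NSICU and that meet the eligibility criteria will be approached for consent to the study", but drug goes only to consented patients who also meet the glucose thresholds.

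The summary lines after section 13 expect 24 enrolled and 24 completing.

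**The concern.** Three nested groups are in play: consented, dosed and completing. They are the same 24 people only if everyone consented is dosed and everyone dosed completes. Otherwise count and percentage can give different answers, and so can the choice of group.

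The errors do not all run one way. Fixed counts applied to more than 24 patients make the goal criterion easier to meet and the two adverse-event criteria harder. Using all consented does the reverse. Undosed patients cannot stop exenatide for nausea and cannot reach goal on it, so they dilute the adverse rates and lower the goal rate.

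No section names completers as the analysis set, but that reading should be ruled out. A patient who stops for good because of nausea before 48 hours would leave the set, and the nausea criterion could then hardly fail. This is not certain, since Table 2 also uses the word discontinue for a stop followed by a restart.

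These criteria are the plan's only formal decision rule, and the study is open-label. An unspecified denominator could be settled after the results are known.

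**Working it through.** **The plan's own figures.** 6/24 = 25.0% and 18/24 = 75.0%, so the stated pairs are correct at N = 24.

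**Where count and percentage part.** In whole patients, the 25% ceiling is floor(0.25N) and the 75% floor is ceil(0.75N).

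| N | Most events allowed at 25% | Fewest at goal for 75% | 18/N |
|---|---|---|---|
| 23 | 5 | 18 | 78.3% |
| 24 | 6 | 18 | 75.0% |
| 25 | 6 | 19 | 72.0% |
| 27 | 6 | 21 | 66.7% |
| 28 | 7 | 21 | 64.3% |
| 30 | 7 | 23 | 60.0% |
| 32 | 8 | 24 | 56.2% |

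The ceiling equals 6 for N = 24 to 27 and the floor equals 18 for N = 23 to 24, so only N = 24 satisfies both. Above 24, the goal criterion breaks at N = 25 and the adverse criteria at N = 28.

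**How likely N is to exceed 24.** The documents give no attrition rate. If 5% or 10% of dosed patients fail to complete (assumed), the chance that at least one of the first 24 does so is 1 − 0.95^24 = 71% or 1 − 0.90^24 = 92%.

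**An illustration with three denominators.** Suppose 36 are consented and 32 dosed.

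- 8 nausea stops: 8/32 = 25.0% and 8/36 = 22.2% both pass; the limit of 6 fails.
- 24 at goal: 24/32 = 75.0% passes and 24 ≥ 18 passes; 24/36 = 66.7% fails.

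**Goal criterion, chance of passing.** Assume 28 dosed, with the number at goal X ~ Binomial(28, g) and undosed patients counted as not at goal.

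| Reading | Needed | g = 65% | 75% | 85% | 95% |
|---|---|---|---|---|---|
| Count of 18 | 18 | 62% | 93% | >99% | >99% |
| 75% of dosed | 21 | 18% | 60% | 95% | >99% |
| 75% of 30 consented (2 undosed) | 23 | 4% | 26% | 76% | >99% |
| 75% of 32 consented (4 undosed) | 24 | 1% | 14% | 59% | 99% |

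With only 25 dosed and g = 75%, needing 18 passes 73% of the time and needing 19 passes 56%.

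**Nausea criterion, chance of passing.** Recruit to 24 completers, with nausea the only cause of non-completion at true rate p. Nausea stops S are then negative binomial (24 completions, completion probability 1 − p). The count rule is S ≤ 6. The percentage rule S/(24 + S) ≤ 0.25 gives S ≤ 8.

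| p | Limit of 6 | 25% of dosed | Limit of 6, with a further 10% stopping for other reasons | 25% of dosed, same |
|---|---|---|---|---|
| 10% | 97% | 99.7% | 96% | 99.7% |
| 20% | 61% | 83% | 49% | 81% |
| 25% | 35% | 59% | 23% | 55% |

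For the last two columns, total stops T are negative binomial with completion probability 1 − p − 0.10, and nausea stops given T are Binomial(T, p/(p + 0.10)).

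If 10% or 20% of consented patients are never dosed, at random, and nausea is the only cause of non-completion, then at p = 25% the rule of 25% of all consented passes 69% or 82% of the time, against 59% on dosed patients.

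**The case against.** The strongest reply is that the plan already answers the question. Section 10.1 defines proportions, section 12 names one set with no exception, and 24 patients are expected both to enroll and to complete. On that reading the rule is a percentage of all consented, and 6 and 18 are just its values at the planned size. The wording in section 10.1 does favour the percentage. But the criteria put the count first and do not refer to section 12. The reading also puts undosed patients in the denominator of endpoints about exenatide.

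Overshoot is not certain either. Methodology 1 asks for completion of the study protocol, and 48 hours is a maximum duration, so a stop directed by the protocol might count as completing. Section 11 is stricter and asks for 48 hours of infusion. Undosed patients may also be few, since eligibility already requires two glucose values above 150 mg/dL.

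The size rests on assumed rates. If reaching the range once counts as achieving the goal, nearly everyone may do so, and at a true 95% the goal readings almost agree. Low gastrointestinal rates with infusion, as the Specific Aims report, would make the nausea readings agree too. This stands as a limit on practical size. It does not remove the contradiction.

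Finally, this is a small descriptive study, and anyone given the raw counts can apply either rule. That is true, but a criterion set in advance to decide on a further trial should give one answer.

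**Conclusion.** The concern holds and should be fixed. That the limits agree only at N = 24 is arithmetic and needs no assumption. From 25 patients on, the goal criterion can pass and fail on the same data.

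How often this would change the decision is uncertain, because the documents give no rate for goal achievement, nausea or attrition. The choice of reading matters a great deal for the goal criterion if the true rate lies between about 65% and 85%, and little near 95%. For nausea it matters at 20% or more and rarely at 10% or below. Severe hypoglycemia has the same limits, so its count and percentage also part at N = 28.

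**What to change.** State in section 10, with a cross-reference in sections 11 and 12, that:

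- all three criteria are scored on every patient who starts exenatide, whether or not the patient completes;
- the 25% and 75% limits bind, and 6 and 18 are only their values at N = 24;
- neither completers nor consented-but-undosed patients define the denominator;
- every nausea discontinuation in that set counts, and a patient who stops before reaching goal counts as not achieving it.

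Recruitment to 24 completers can continue for the pharmacokinetic and continuous glucose data.

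The cost is protocol and SAP wording. These three criteria would depart from the all-consented set in section 12, observed rates may look slightly less favourable, and some patients in the decision set will have incomplete 48-hour profiles. The change does not settle what counts as achieving the goal, which needs its own definition.

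### Continuous outcomes are to be reported as mean ± SE while proportions get 95% CIs, so a study meant to describe patients plans no measure of between-patient spread (minor reporting fix)

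*Combined protocol and SAP*

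**What the plan says.** Section 12 (Data analysis plan) states that "Descriptive statistics will be performed" and then fixes the format: means ± "standard error (SE) or success rates and corresponding 95%CI for continuous and" "dichotomous outcomes, respectively". The closing word assigns the SE to continuous outcomes and the 95% CI to dichotomous ones. The same section has the data checked for outliers and asymmetry beforehand, with transformation where suitable.

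Section 10.2 gives the purpose of the continuous endpoints: "The following descriptive endpoints are included for describing experience with exenatide use in the NSICU population". They include average glucose, percent time in range, time to goal, insulin per kg, episode counts and, in the monitored subset, percent time outside microdialysis limits. For time to goal and insulin use, section 10.2 itself specifies a mean.

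Two items could be mistaken for a measure of spread. The SD in "variability outcome (SD)-MADGE" belongs to a glycemic variability endpoint. The daily medians in the microdialysis protocol (Methodology, item 5) are calculated within each patient. Neither shows how patients differ from one another on the other endpoints.

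**The concern.** An SE answers how well the mean is known. An SD, IQR or range answers how much patients differ, which is what a descriptive single-arm study is asked to show. The protocol's own rationale (Specific Aim 1) is to control mean glucose while limiting variability and strictly avoiding hypoglycemia. A favourable mean could sit alongside a few patients who did badly, and mean ± SE would not reveal that.

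There is also an inconsistency within the report. A reader who sees 95% CIs on proportions may read the ± figures on means in the same way, although they are about half as wide as 95% limits. Finally, section 10.2 says the results will inform whether an efficacy trial follows, and planning such a trial would call for SDs.

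**Working it through.** **The plan's own figures.** Section 11 plans on 24 completers: "we determined to enroll 24 patients who complete 48 hours of exenatide infusion and continuous glucose monitoring". No SD, precision target, alpha or power is given, so 24 cannot be re-derived. The arithmetic around it is consistent: 6/24 = 25%, 18/24 = 75%, and 200 × 15–20% = 30–40 per year. The documents give no SE or SD for any continuous outcome, so there is no such figure to reproduce.

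**Inputs.** n = 24 from section 11. The actual n may differ, because "An intent-to-treat analysis (defined as all individuals consented in the study) will be utilized". The microdialysis subset has no stated size ("In eligible patients, cerebral microdialysis monitoring will also be performed"), so a range is shown as an assumption.

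**Step 1: SE relative to SD.** SE/SD = 1/√n = 1/√24 = 1/4.90 = 0.204.

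**Step 2: confidence level of mean ± 1 SE.** P(|t| < 1) with n − 1 = 23 df is 67.2%. The large-sample limit is 68.3%.

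**Step 3: 95% CI for a mean.** The half-width is t(0.975, 23) × SE = 2.069 × 0.204 SD = 0.422 SD, about twice ± 1 SE.

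**Step 4: share of patients covered.** If values are normal, mean ± 1 SE spans 2Φ(0.204) − 1 = 16% of patients. Mean ± 1 SD spans 68%.

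**Step 5: illustration in mg/dL.** The SDs are assumed and are not in the documents; n = 24.

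| Assumed SD | SE | 95% CI half-width |
|---|---|---|
| 20 | 4.1 | 8.4 |
| 30 | 6.1 | 12.7 |
| 40 | 8.2 | 16.9 |

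**Step 6: other sample sizes.** The sizes below 24 show a possible microdialysis subset. The 30 shows an analysis set larger than the completers. Both are assumptions.

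| n | SE/SD | Level of mean ± 1 SE | 95% multiplier |
|---|---|---|---|
| 4 | 0.50 | 60.9% | 3.18 |
| 5 | 0.45 | 62.6% | 2.78 |
| 6 | 0.41 | 63.7% | 2.57 |
| 8 | 0.35 | 64.9% | 2.36 |
| 12 | 0.29 | 66.1% | 2.20 |
| 24 | 0.20 | 67.2% | 2.07 |
| 30 | 0.18 | 67.4% | 2.05 |

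**Step 7: zeros.** Under Table 2, subcutaneous insulin is given only for glucose above 180 mg/dL from the second hourly check. A patient who stays at or below that level from then on has insulin use of exactly zero. Episode counts can also be zero. A transformation sends every zero to the same value, so any cluster remains. How large it would be cannot be judged from the documents.

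**The case against.** A correctly labelled SE is not an error. If n is given with each mean, the SD of an untransformed outcome is SE × √n, so planners could recover it. Planning descriptive statistics does not forbid an SD or a median, and section 12 does look for asymmetry. All of this stands, and it is why the point is minor. The recovery has limits, though. It needs the n for each outcome, which may not be 24; it fails for transformed data; and a recovered SD still describes a skewed outcome poorly.

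A reader might infer three stronger things that the documents do not support:

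- **That mean ± SE is only a 63% interval in this trial.** That level requires about 5 or 6 patients. Such a number might apply to microdialysis, but the documents never state it, and at that size the SE is 0.41–0.45 of the SD rather than one-fifth.
- **That zero severe hypoglycemic events would be reported with a 0–0% interval.** Section 12 names no method for its 95% CIs, so it does not commit to the normal approximation that gives this result. An exact interval for 0/24 is 0 to 1 − 0.025^(1/24) = 14.2%. The unnamed method is a missing detail. Nor can zero events be called likely from the cited stroke series: it had eleven patients, used subcutaneous dosing and reported symptomatic events.
- **That the decision on an efficacy trial is distorted.** The section 10.2 criteria are patient counts (at most 6, at least 18, at most 6). No SE or CI enters them.

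**Conclusion.** The point holds as a minor reporting weakness. The summary that section 12 prescribes for continuous outcomes does not serve the descriptive purpose in section 10.2, and no other section supplies between-patient spread or a 95% interval for those outcomes. At n = 24, the SE is about one-fifth of the SD, and mean ± 1 SE is about a 67% interval, against ± 2.07 SE for 95%.

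The SE/SD ratio depends only on n. The 67% and 2.07 figures also assume approximate normality and 24 analysed patients; at n = 30 they barely change (67.4% and 2.05). The remark about zeros is conditional on their occurring. The feasibility conclusion is unaffected. What is affected is how fully the descriptive results portray patients, and whether SDs are directly available for the next trial.

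**What to change.** In section 12, replace mean ± SE for continuous outcomes with *mean (SD) with 95% CI*. Add *median (IQR, range)* for skewed, bounded or count outcomes: time to goal, insulin use, percent-time measures and episode counts. Section 10.2 names means for time to goal and insulin use, so either report the medians alongside those means or amend section 10.2 to match. Changing section 12 alone to medians would set the two sections against each other. State n with every summary.

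Optionally, name exact (Clopper-Pearson) 95% CIs for the proportions.

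The cost is a few lines of wording, with no new data, patients or procedures. The only downside is that the reported intervals will look wider.
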